6.1. Study Description and Duration

The study consists of 3 periods: a screening/baseline period, a vaccine response assessment period, and a follow-up period. The study design is depicted in [Figure 2](#) and [Figure 3](#); study treatment assignment is depicted in [Figure 1](#). The Schedules of Events can be found in [Table 3](#) (enrollment wave 1 [study arms 1, 2, 3, and 6a] and enrollment wave 3 [arms 7, 8, and 6c]), [Table 4](#) (enrollment wave 2 [study arms 4, 5, and 6b]), and [Figure 3](#) (enrollment wave 4 [arms 9 and 6d]).

Subjects will be assessed for eligibility during the **screening/baseline period**, which may occur up to 21 days prior to day 1. To be eligible for the study, subjects must be confirmed negative for current or past SARS-CoV-2 infection by both RT-PCR and serology tests (refer Section [7.2.2](#) for exclusion criteria).

During this period, subjects will also be assigned to an enrollment wave, as described in Section [8.5](#).

On day 1, eligible subjects will be randomized to a study arm (1 of 12) within their assigned enrollment wave. Subjects randomized to study arms 1 through 5 or 7 through 9 will receive an IV infusion or SC injection of the study drug (REGN10933+REGN10987) on day 1 or day 7. Subjects in arms 6a to 6d (the control arms) will not receive any study drug. The first dose of the vaccine will be administered on day 1 or day 15, based on study arm assignment at randomization ([Figure 1](#)).

All subjects will receive the second dose of the vaccine 28 days after their first dose of the vaccine in accordance with the EUA Fact Sheet ([Moderna COVID-19 Vaccine \[HCP Fact Sheet\], 2022](#)) (refer to Section [3.2.1](#) for rationale). Refer to Section [8.5](#) for more information on dose levels and timing of administration.

The **vaccine response assessment period** represents the time period of the primary analysis (Section [4.1](#)). For study arms 1, 2, 3, 7, 8, 6a, and 6c, this period includes up to study day 71; for study arms 4, 5, 9, 6b, and 6d, the period includes up to day 57. Following this assessment period, subjects will enter a **follow-up period** lasting up to 10 months.

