8.5. Method of Enrollment and Treatment Assignment

Site-managed assignment. At screening, eligible subjects will be assigned to an enrollment wave. The enrollment waves are intended to avoid or minimize the potential for unused doses of Moderna mRNA-1273 COVID-19 vaccine (refer to Section 3.2.1 for additional rationale). Every effort should be made by sites to avoid unused doses of vaccine.

Sites will manage the placement of subjects into each wave. Every effort should be made by the site to ensure balance of age (<65 years and \geq 65 years) within each of the enrollment waves.

Randomization. At baseline (day 1), subjects will be randomized to the corresponding study arms in each wave as described in [Table 2](#).

Randomization will be performed according to a computer-generated randomization scheme provided by an interactive web response system (IWRS) to a designated study pharmacist or a qualified designee.

Randomization will be stratified by age (<65 years versus \geq 65 years).

Table 2: Study Treatment Assignment

Study Arm	Randomization Ratio	Targeted Enrollment	Co-administered REGN10933+REGN10987 Combination Therapy	Moderna mRNA-1273 Vaccine*
Enrollment Wave 1				
1	2	30	1200 mg (600 mg of each mAb) IV on day 1	On day 15 and day 43
2	2	30	300 mg (150 mg of each mAb) IV on day 1	On day 15 and day 43
3	2	30	150 mg (75 mg of each mAb) IV on day 1	On day 15 and day 43
6a	1	15	None	On day 15 and day 43
Enrollment Wave 2				
4	2	30	1200 mg (600 mg of each mAb) SC on day 1	On day 1 and day 29
5	2	30	600 mg (300 mg of each mAb) SC on day 1	On day 1 and day 29
6b	1	15	None	On day 1 and day 29
Enrollment Wave 3				
7	15	30	48 mg (24 mg of each mAb) IV on day 1	On day 15 and day 43
8	15	30	12 mg (6 mg of each mAb) IV on day 1	On day 15 and day 43
6c	4	8	None	On day 15 and day 43
Enrollment Wave 4				
9	15	30	1200 mg (600 mg of each mAb) IV on day 7	On day 1 and day 29
6d	4	8	None	On day 1 and day 29

*Moderna mRNA-1273 vaccine will be administered as described on the EUA Fact Sheet ([Moderna COVID-19 Vaccine \[HCP Fact Sheet\], 2022](#)).

mAb=monoclonal antibody; SC=subcutaneous; IV=intravenous.

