Study arms 6a, 6b, 6c, and 6d (receiving no study drug): No blood for assessment of drug concentration in serum will be collected.

11. The window for pre-dose ADA sample collection should be as close to administration of study drug as is reasonable. Actual dosing time and ADA sample collection times will be recorded.
- Study arms 6a, 6b, 6c, and 6d (receiving no study drug):** No blood for ADA assessment will be collected.
12. Adverse events will be continuously monitored as described in Section 10.1.1.
13. **For Arms 1, 2, 3, 6a, 6c, 7 and 8:** For subjects receiving their COVID-19 vaccine booster as part of the sub-study, the vaccine booster may be administered at any time from 5 months after their second vaccine dose until study day 345. The *actual date* the subject received their second vaccine dose should be used (as opposed to using study day 43) to determine when the booster window should begin.
14. **For Arms 4, 5, 6b, 6d, and 9:** For subjects receiving their COVID-19 booster as part of the sub-study, the vaccine booster may be administered at any time from 5 months after their second vaccine dose until study day 331. The *actual date* the subject received their second vaccine dose should be used (as opposed to using study day 29) to determine when the booster window should begin.

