4.6. Safety Variables

4.6.1. Adverse Events and Serious Adverse Events

Adverse events and serious adverse events will be collected from the time of informed consent signature and then at each visit until the end of the study. All adverse events are to be coded to a PT and associated SOC according to the latest version of MedDRA®.

For safety variables, the following observation periods are defined:

- The **pre-vaccination period** is defined as the time from study drug administration to the first vaccine dose administration.
- The **primary series vaccination period** is defined as the time from the first vaccine dose administration to 28 days after the second vaccine dose administration, and in subjects receiving only one dose of the vaccine, 28 days after the first vaccine dose administration.

- The **post primary series vaccination period** is defined as the time from the end of the primary series vaccination period to the end of the follow-up period in subjects who do not receive the sub-study provided vaccine booster. In subjects who receive the sub-study provided vaccine booster dose, the post-primary series vaccination period is defined as the time from the end of the primary series vaccination period to the administration of the sub-study provided vaccine booster.
- The **post-booster vaccination period** is defined as the time from the sub-study provided vaccine booster to the end of the follow-up period.

Treatment-emergent adverse events are defined as those that are not present at the time of the first dose of Moderna mRNA-1273 Vaccine or REGN10933+REGN10987 (as applicable and whichever occurs first) or represent the exacerbation of a pre-existing condition.

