5.8.1. Adverse Events

All AEs reported in this study will be coded using the currently available version of MedDRA®. Coding will be to lowest level terms. The PT and the primary SOC will be listed.

All adverse events will be provided in a listing. Listing of deaths and other SAEs will also be provided.

Tabulations by treatment group will include the following:

All periods combined

- Overview of TEAEs
- TEAEs by SOC and PT
- TEAEs by SOC and PT and Severity
- Serious TEAEs by SOC and PT
- Study Drug Related TEAEs by SOC and PT
- Vaccine Related TEAEs by SOC and PT
- Study Drug Related Infusion Related Reaction TEAEs by SOC and PT

- Study Drug Related Injection Site Reaction TEAEs by SOC and PT
- Vaccine Related Injection Site Reaction TEAEs by SOC and PT
- Study Drug Related Hypersensitivity Reaction TEAEs by SOC and PT
- Vaccine Related Hypersensitivity Reaction TEAEs by SOC and PT
- Treatment-Emergent AESIs by SOC and PT
- TEAEs leading to permanent discontinuation of vaccine by SOC and PT
- TEAEs leading to permanent discontinuation of study drug by SOC and PT
- TEAEs leading to death by SOC and PT

Pre-vaccination period

- Overview of TEAEs
- TEAEs by SOC and PT
- TEAEs by SOC and PT and Severity
- Serious TEAEs by SOC and PT
- Study Drug Related TEAEs by SOC and PT
- Study Drug Related Infusion Related Reaction TEAEs by SOC and PT
- Study Drug Related Injection Site Reaction TEAEs by SOC and PT
- Study Drug Related Hypersensitivity Reaction TEAEs by SOC and PT
- TEAEs leading to permanent discontinuation of study drug by SOC and PT
- TEAEs leading to death by SOC and PT

Primary series vaccination period and Post-booster vaccination period

- Overview of TEAEs
- TEAEs by SOC and PT
- TEAEs by SOC and PT and Severity
- Serious TEAEs by SOC and PT
- Study Drug Related TEAEs by SOC and PT
- Vaccine Related TEAEs by SOC and PT
- Study Drug Related Infusion Related Reaction TEAEs by SOC and PT
- Study Drug Related Injection Site Reaction TEAEs by SOC and PT
- Vaccine Related Injection Site Reaction TEAEs by SOC and PT
- Study Drug Related Hypersensitivity Reaction TEAEs by SOC and PT
- Vaccine Related Hypersensitivity Reaction TEAEs by SOC and PT

- TEAEs leading to permanent discontinuation of vaccine by SOC and PT
- TEAEs leading to permanent discontinuation of study drug by SOC and PT
- TEAEs leading to death by SOC and PT

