11. The window for pre-dose ADA sample collection should be as close to administration of study drug as is reasonable. Actual dosing time and ADA sample collection times will be recorded.

Study arms 6a, 6b, 6c, and 6d (receiving no study drug): No blood for ADA assessment will be collected.

12. Adverse events will be continuously monitored as described in Protocol Section 10.1.1.

13. For Arms 1, 2, 3, 6a, 6c, 7 and 8: For subjects receiving their COVID-19 vaccine booster as part of the sub-study, the vaccine booster may be administered at any time from 5 months after their second vaccine dose until study day 345. The actual date the subject received their second vaccine dose should be used (as opposed to using study day 43) to determine when the booster window should begin.
14. For Arms 4, 5, 6b, 6d, and 9: For subjects receiving their COVID-19 booster as part of the sub-study, the vaccine booster may be administered at any time from 5 months after their second vaccine dose until study day 331. The actual date the subject received their second vaccine dose should be used (as opposed to using study day 29) to determine when the booster window should begin.

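### Post-booster TEAE percentages depend on booster date, because the post-booster period runs to the end of follow-up (nominally 35 to 185 days) and no fixed window or person-time rate is planned

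*SAP*

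**What the plan says.** SAP 4.6.1 splits safety observation into four periods. The primary-series period "is defined as the time from the first vaccine dose administration to 28 days after the second vaccine dose administration", or ends 28 days after the first dose if only one is given. The post-booster period "is defined as the time from the sub-study provided vaccine booster to the end of the follow-up period". Protocol 11.4.6.1 draws the same boundaries.

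SAP 5.8.1 gives one list of TEAE tables, by treatment group, under the joint heading "Primary series vaccination period and Post-booster vaccination period". Protocol 11.4.6.1 states the measure: number and percentage of subjects with at least one event. SAP 5.6 tabulates the time from dose 2 to booster, but the TEAE tables do not use it. Neither document gives an exposure-adjusted rate or a fixed post-booster window for these tables.

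For arms 1, 2, 3, 6a, 6c, 7 and 8, SAP 11.1 (footnote 13) says "the vaccine booster may be administered at any time from 5 months after their second vaccine dose until study day 345". For arms 4, 5, 6b, 6d and 9, Protocol 9.1.1 (footnote 14) says "the vaccine booster may be administered at any time from 5 months after their second vaccine dose until study day 331".

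**The concern.** A crude percentage of subjects with at least one event cannot fall as observation lengthens, and it rises whenever late events occur. With an open-ended period, a subject boosted early has several times as long to record an unrelated illness as one boosted late. The post-booster all-cause, severity and serious TEAE tables would then reflect when people were boosted as well as how they tolerated the booster.

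Two readings are exposed. One is between arms in different waves, since booster dates may differ by wave and each active arm sits in a single wave. The other is an informal reading of the post-booster tables beside the primary-series tables, which share a list but not an observation length. The SAP moves late events after dose 2 into a separate post-primary-series period, but leaves late events after the booster in the post-booster period.

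**Working it through.** **Inputs.**
- Dose days (Protocol 8.5): waves 1 and 3 "On day 15 and day 43"; waves 2 and 4 on days 1 and 29.
- Dose interval (Protocol 6.1): "All subjects will receive the second dose of the vaccine 28 days after their first dose of the vaccine".
- Last visit (schedules of events): day 380 for waves 1 and 3, day 366 for waves 2 and 4, each ±14 days.
- Last booster day: 345 or 331.
- Five months is taken as 152 days.

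**The plan's own figure.** Last booster day = last visit − 35: 380 − 35 = 345 and 366 − 35 = 331. Both reproduce. (The text asks for more than 35 days; these days leave exactly 35.)

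**Length of the post-booster period.**
- Shortest: 380 − 345 = 35; 366 − 331 = 35.
- Longest, waves 1 and 3: first booster day 43 + 152 = 195; 380 − 195 = 185.
- Longest, waves 2 and 4: first booster day 29 + 152 = 181; 366 − 181 = 185.
- Ratio: 185/35 = 5.3.
- With five months as 150 to 153 days, the longest is 187 to 184. With the ±14-day last-visit window, the extremes are about 21 and 201 days.

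**Length of the primary-series period.** 28 + 28 = 56 days, covering two doses.

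**Effect on the percentage.** The documents give no background TEAE rate. Assume a constant rate r per person-year, r = 1 with range 0.5 to 2. Then P(at least one background TEAE) = 1 − exp(−r × days/365).

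| Window | r = 0.5 | r = 1 | r = 2 |
|---|---|---|---|
| 28 days | 4% | 7% | 14% |
| 35 days | 5% | 9% | 17% |
| 56 days | 7% | 14% | 26% |
| 185 days | 22% | 40% | 64% |

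For example, at r = 1: 1 − exp(−35/365) = 0.09 and 1 − exp(−185/365) = 0.40.

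**Possible difference between waves.** The booster sub-study came with Amendment 5, dated 28 January 2022 (SAP 1.2.6). The wave 3 and 4 arms came with Amendment 4, dated 21 July 2021. Enrolment dates are not given. If a wave 1 subject was randomised on 29 April 2021 (assumption), 28 January 2022 is study day 275, so the longest possible post-booster period is 380 − 275 = 105 days. A wave 3 subject randomised on 21 July 2021 (assumption) would be at day 192, before the first booster day, so 185 days remain possible. These are upper limits, not expected lengths.

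**The case against.** The study is descriptive, with no hypothesis testing (Protocol 11.1). The safety objective concerns drug and vaccine given in close succession, and the only booster objective is immune response (Protocol 2.3). The open-ended period also serves a purpose: TEAE and SAE endpoints run throughout the study, and the periods leave no gap in follow-up. All of that stands, and it limits the consequence.

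Booster tolerability is also partly separable already. SAP 5.8.1 includes vaccine-related TEAE, injection-site and hypersensitivity tables for this period, and AESIs have fixed day-4 and day-29 windows (SAP 4.6.2). This largely stands for acute reactions. It does not help the all-cause, severity and serious tables. The related tables have a small leak: under SAP 6.3, a TEAE with missing vaccine causality counts as related whenever it follows the first vaccine dose, however late.

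A reader might infer more than the documents support:
- That the SAP plans a safety comparison of booster against primary series. It does not; the joint heading is a list of outputs.
- That comparisons between arms in general are distorted. Arms within a wave were randomised together, each wave with its own vaccine-only arm (Protocol 3.2.1.9), and share calendar time. The calendar mechanism therefore bears mainly on contrasts across waves.
- That the period should simply be cut at 28 days. SAP 5.8.1 has no tables for a later period, so later events, including SAEs, would remain only in the all-periods tables and the listings. The definition would also depart from Protocol 11.4.6.1.

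**Conclusion.** The point holds as one about descriptive tables. The range of 35 to 185 days follows from the documents. So does the direction: the all-cause, severity and serious post-booster percentages depend on booster date and mix booster reactions with background illness. The damage is to contrasts across waves and to informal comparison with the primary-series tables.

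The size is conditional. The 9% (5 to 17%) against 40% (22 to 64%) rests on an assumed constant rate of 1 TEAE per person-year (0.5 to 2) and takes the two extremes of booster date. Actual booster dates, uptake and enrolment dates are not in the documents, so a real difference between waves is plausible but not shown. No planned inference changes.

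**What to change.** In SAP 4.6.1, add a fixed window from the sub-study booster to 28 days after it, and run the SAP 5.8.1 post-booster TEAE tables on that window. Keep the existing booster-to-end-of-follow-up period as a second tabulation, with a note that its length varies by subject, so that late events, including SAEs, stay in a period-specific table. Record the addition in SAP 1.2.5.

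Nearly every booster recipient who completes follow-up would then have equal time, because even the last permitted booster leaves 35 nominal days. An early last visit after a very late booster could leave about 21.

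The SAP should also say that a 28-day, one-dose window is still not directly comparable with the nominal 56-day, two-dose primary-series period. At the assumed rate of 1 per person-year, background alone is about 7% against 14%.

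The cost is one extra derived flag and one extra set of tables, with no new data.

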3.3.1. Risk-Benefit for REGN10933+REGN10987

The anticipated risks and benefits of casirivimab and imdevimab are informed by pre-clinical and clinical data, including data from phase 3 trials. For additional information concerning clinical and pre-clinical data, refer to the Investigator's Brochure.

Intravenous Administration of Casirivimab+Imdevimab in Clinical Trials. In COV-2067, the phase 3 outpatient treatment trial, a single intravenous dose of casirivimab and imdevimab was shown (relative to placebo) to reduce COVID-19-related hospitalizations or all-cause death by 71.3% (2400 mg dose) and 70.4% (1200 mg dose), reduce symptom duration by 4 days (2400 mg and 1200 mg), and reduce viral load over the first 7 days. Serious adverse events occurred more frequently in the placebo group (4.0%) than in either treatment group (2400 mg, 1.1%; 1200 mg, 1.3%), and grade ≥ 2 infusion-related reactions were infrequent (<0.3% in all groups)

([Weinreich, 2021b](#)). Similar virologic efficacy and a similar safety profile were observed in the phase 1/2 portion of this trial, which evaluated casirivimab and imdevimab at 8000 mg and 2400 mg IV doses ([Weinreich, 2021a](#)).

Subcutaneous Administration of Casirivimab+Imdevimab in Clinical Trials. In COV-2069, the phase 3 prevention trial in those at high risk of infection by a household contact, a single subcutaneous dose of casirivimab and imdevimab (1200 mg) reduced (relative to placebo) symptomatic SARS-CoV-2 infection by 81.4%, and reduced overall SARS-CoV-2 infection by 66.4%. Serious adverse events occurred at similar frequencies in the treatment group (1%) and placebo group (1%). Injection-site reactions were more common in the treatment group (4%) compared to the placebo group (2%), but no injection-site reactions in the study were grade 3 or above. The majority of injection site reactions occurred within one day and resolved within two days ([O'Brien, 2021b](#)).

Among a sub-group of individuals in COV-2069 who were identified as SARS-CoV-2 positive but asymptomatic during screening, a single subcutaneous dose of casirivimab and imdevimab (1200 mg) reduced (relative to placebo) progression to symptomatic disease by 31.5%, and reduced the duration of symptoms in those that developed symptomatic infections. Injection-site reactions were more common in the treatment group (4%) compared to the placebo group (1%), but no injection-site reactions in the study were grade 3 or above ([O'Brien, 2021a](#)).

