1.2.3. Exploratory Objectives

The exploratory objectives of the study are:

- To explore circulating T cell and B cell responses to SARS-CoV-2 antigens in subjects who receive both REGN10933+REGN10987 and Moderna mRNA-1273 vaccine versus those who receive the vaccine alone
- To explore the impact of REGN10933+REGN10987 as measured by the induction of vaccine-induced binding antibodies to SARS-CoV-2 receptor-binding domain (RBD) antigens post-Moderna mRNA-1273 vaccination that compete with the same epitopes recognized by REGN10933 and/or REGN10987

- To explore how REGN10933+REGN10987 alters vaccine-induced neutralizing antibody responses, induced by Moderna mRNA-1273 vaccine, against SARS-CoV-2 variants
- To characterize viral variants by sequencing SARS-CoV-2 in subjects who become infected post-baseline
- To explore the impact on vaccine responses and the mechanism of action of REGN10933+REGN10987 as measured by experimental laboratory assays and biomarkers after vaccination with Moderna mRNA-1273
- To explore biomarkers and genomic factors associated with safety and immune responses after exposure to REGN10933+REGN10987 and Moderna mRNA-1273
- To assess immune responses in subjects who receive booster vaccinations during the study

1.2.4. **Endpoints**

Primary Endpoint

The primary endpoint is the 50% inhibitory dilution (ID₅₀) titers of vaccine-induced neutralizing antibodies to the SARS-CoV-2 S protein assessed 56 days after the first dose of Moderna mRNA 1273 vaccine.

This endpoint will be used in assessing both primary objectives.

Secondary Endpoints

- Absolute values, change from baseline, and percentage change from baseline in concentrations of vaccine-induced antibodies to the following SARS-CoV-2 antigens over time:
 - Anti-S protein
 - Anti-RBD
 - Other S protein subdomains (including S1, S2, and NTD)
- 50% inhibitory dilution (ID₅₀) titers of vaccine-induced neutralizing antibodies to SARS-CoV-2 S protein assessed over time after the first dose of Moderna mRNA-1273 vaccine
- Proportion of subjects with treatment-emergent adverse events (TEAEs) throughout the study
- Proportion of subjects with treatment-emergent serious adverse events (SAEs) throughout the study
- Proportion of subjects with infusion-related reactions (grade ≥ 2) to REGN10933+REGN10987 through day 4 post-infusion
- Proportion of subjects with injection site reactions (grade ≥ 3) to REGN10933+REGN10987 or each dose of Moderna mRNA-1273 vaccine through day 4 post-injection

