3.4. Safety Analysis Set (SAF)

The safety analysis set (SAF) includes all randomized subjects who have been vaccinated with at least one dose or received any study drug; it is based on the treatment received (as treated). Treatment compliance/administration and all clinical safety variables will be analyzed using the SAF.

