3.5. Vaccine Booster Analysis Set

The vaccine booster analysis set includes Per Protocol Set subjects who signed the optional sub-study informed consent, have been vaccinated with the study-provided vaccine booster and did not have an adverse event of COVID (Preferred Terms of ‘COVID-19’, ‘Asymptomatic COVID-19’, ‘SARS-CoV-2 test positive’, ‘COVID-19 pneumonia’) or a positive PCR test prior to the post-booster follow-up sample collection.

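### COVID-19 counts as a TEAE, so the any-TEAE proportion by arm mixes tolerability with prevention of infection, and no table without COVID-19 is planned (minor)

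*SAP*

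**What the plan says.** - **Definition.** SAP 4.6.1: "Treatment-emergent adverse events are defined as those that are not present at the time of the first dose of Moderna mRNA-1273 Vaccine" or of REGN10933+REGN10987, whichever is first, plus exacerbations of existing conditions. Protocol 11.4.6.1 agrees. Neither sets COVID-19 apart.
- **COVID-19 as an adverse event.** SAP 3.5 limits the booster set to subjects who "did not have an adverse event of COVID". It names four preferred terms, covering COVID-19, its asymptomatic form, COVID-19 pneumonia and a positive SARS-CoV-2 test.
- **Population.** The safety set "includes all randomized subjects who have been vaccinated with at least one dose or received any study drug" (SAP 3.4). Infected subjects stay in. The per protocol set (SAP 3.1) and the booster set remove them.
- **Endpoints.** SAP 1.2.4 lists "Proportion of subjects with treatment-emergent adverse events (TEAEs) throughout the study" and "Proportion of subjects with treatment-emergent serious adverse events (SAEs) throughout the study".
- **Drug effect.** Protocol 3.3.1 reports that one 1200 mg subcutaneous dose in household contacts (COV-2069) reduced "symptomatic SARS-CoV-2 infection by 81.4%, and reduced overall SARS-CoV-2 infection by 66.4" per cent.
- **Tables.** SAP 5.8.1 plans an overview and tables by SOC and PT, severity, seriousness, relatedness to drug and to vaccine, and AESI, plus a full listing. None omits COVID-19. SAP 4.6.5 names SARS-CoV-2 test results as a safety variable, but SAP 5.8 gives no analysis of them.

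**The concern.** The secondary safety objective asks how well drug and vaccine are tolerated in close succession. A subject whose only event is COVID-19 counts in the any-TEAE proportion exactly as a subject with a reaction does. If the drug prevents infections, drug arms lose some of those subjects. A real excess of other events could then be partly offset in that one summary figure.

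Two features of the plan make this harder to see. First, a subject can have several events, so the proportion with any non-COVID TEAE cannot be obtained by subtracting preferred-term rows. Second, the post-primary-series period has no table of its own. For a subject on schedule without a sub-study booster, it runs from day 56 to day 365 after the first vaccine dose, 309 of 365 days. Infections in that period enter only the tables for all periods combined.

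**Working it through.** **Plan's own figure.** The documents give no precision for TEAE or SAE proportions. Their precision figures concern titres. For 30 v 46 subjects, 1.969 × 0.30 × √(1/30 + 1/46) = 0.139, which matches the stated 0.14 log. Arm sizes also agree: 8 × 30 + 15 + 15 + 8 + 8 = 286.

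**Inputs.**
- e, protection: 81.4% (symptomatic) or 66.4% (all infections), from Protocol 3.3.1.
- c, risk of recorded COVID-19 without drug: not given for this trial. Assumed 2% to 20%. The only placebo rate in the documents is 9.3%, in COV-2069 adolescents.
- b, risk of any non-COVID TEAE: not given. Assumed 40% to 80%.
- COVID-19 and other events are assumed independent.

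**Any TEAE.** Control: pC = 1 − (1 − b)(1 − c). Drug: pD = 1 − (1 − b)(1 − c(1 − e)). The non-COVID excess that would just be offset is x = (1 − b)[1 − (1 − c)/(1 − c(1 − e))]. The half-width is 1.96 × √(pC(1 − pC)/46 + pD(1 − pD)/30). With e = 81.4%:

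| b | c | Control % | Drug % | Difference (points) | Offset excess (points) | 95% half-width (points) |
|---|---|---|---|---|---|---|
| 40% | 2% | 41.2 | 40.2 | −1.0 | 1.0 | 22.6 |
| 40% | 20% | 52.0 | 42.2 | −9.8 | 10.1 | 22.8 |
| 60% | 9.3% | 63.7 | 60.7 | −3.0 | 3.1 | 22.3 |
| 80% | 2% | 80.4 | 80.1 | −0.3 | 0.3 | 18.3 |
| 80% | 20% | 84.0 | 80.7 | −3.3 | 3.4 | 17.6 |

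Over the same grid, e = 66.4% gives −0.3 to −8.0 points. With e = 0 the difference is 0. An assumed e = −20% (impaired vaccine response) gives +0.1 to +2.4 points, against the drug arms. If all 240 drug subjects were pooled against 46 controls, the half-width would be about 12 to 16 points.

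**Why subtraction fails.** In the 60%/9.3% row, controls show 63.72 − 9.30 = 54.42%. The drug arm shows 60.69 − 1.73 = 58.96%. The true non-COVID proportion is 60% in both, so subtraction creates a spurious difference of about 4.5 points the other way.

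**Any SAE.** Assume a 1% non-COVID SAE risk and that 1% to 5% of COVID-19 cases are serious. The extreme case (c = 20%, 5% serious) gives 1 − 0.99 × (1 − 0.20 × 0.05) = 1.99% in controls. In a drug arm it gives 1 − 0.99 × (1 − 0.20 × 0.186 × 0.05) = 1.18%, a difference of −0.81 points. The smallest case is −0.02. Expected COVID-19 SAEs among 46 controls are at most 46 × 0.20 × 0.05 = 0.46, while a single SAE in 46 is already 2.2 points.

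**Start of counting.** In waves 1 and 3 TEAEs count from day 1 in drug arms but from the first vaccine dose, day 15, in 6a and 6c: 379 v 365 days to study day 380. At an assumed constant hazard h of 0.2% to 1% per day, 1 − exp(−14h) = 2.8% to 13.1% of drug-arm subjects have an event in the extra 14 days. Many would have had one later anyway. The shift in the whole-study proportion is exp(−365h) × (1 − exp(−14h)), which is 0.482 × 0.0276 = 1.3 points at 0.2% and 0.026 × 0.131 = 0.3 points at 1%. It runs against the drug arms.

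**The case against.** Several readings stronger than this point are tempting, and the documents do not support them.

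- **That the TEAE comparison favours the drug arms.** This is not established. Five of the eight drug arms receive less than 1200 mg, with no preventive figure for those doses, and only arm 4 matches both the dose and the route behind the 81.4%. Every subject is vaccinated. Protocol Table 1 matches 12 mg at day 15 to day 169 after 1200 mg, a level set by 1% of the dose, so drug is low for much of the year. Protocol 3.3.1 does not expect activity against Omicron, and Protocol 3.2.1.2 allows that vaccine response may be altered. The earlier start of counting in waves 1 and 3 also runs the other way.
- **That SAEs show the pattern.** Protocol 3.3.1 says "Serious adverse events occurred more frequently in the placebo group (4.0%) than in either treatment group" (1.1% and 1.3%), but that trial treated infected outpatients. Subjects here must test negative at entry. The prevention trial in the same section shows SAEs of 1% v 1%.
- **That an excess of related events could be hidden.** The drug-related and vaccine-related tables, the AESI table and the SOC/PT tables show such events separately, and prevented infections cannot cancel them there.

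It is also fair that SAP 5.8.1 plans only descriptive tabulations, without differences or intervals. Protocol 10.1.1 makes isolated test findings adverse events only under conditions, so not every asymptomatic positive need be recorded as one.

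These arguments limit the size of the problem and do not remove it. No planned table gives the proportion with any non-COVID TEAE, and opposing biases of unknown size do not make the total interpretable.

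**Conclusion.** The point holds as a minor one, confined to the all-cause summary proportions. The any-TEAE proportion mixes tolerability with prevention of infection, and the plan offers no figure free of that mixture. The shift can favour a drug arm while the virus is susceptible and drug is present: about 0 to 10 points, or 3.0 points at a 60% non-COVID TEAE rate and a 9.3% COVID-19 rate. It is nil where the drug does not protect and could reverse. It is below the half-width of any single-arm comparison, but it is systematic, so more subjects would not remove it. For SAEs it is probably under 1 point. These sizes rest on assumed TEAE, COVID-19 and seriousness rates, on independence, and on carrying the COV-2069 protection over to vaccinated subjects, which probably overstates it.

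**What to change.** Keep all planned tables. In SAP 5.8.1, for all periods combined, add:

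1. the TEAE overview with the four preferred terms of SAP 3.5 removed;
2. the serious-TEAE table with the same terms removed;
3. a table by arm of COVID-19 adverse events and positive RT-PCR results, which also gives the SAP 4.6.5 variable an analysis.

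The first two make the contribution of events coded to those terms zero by construction. They do not alter the different start of counting in waves 1 and 3, which a table footnote can state. The cost is SAP wording and two or three extra descriptive tables. No new data are needed, and the term list already exists, so naming it in the SAP avoids a post hoc choice.
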